811 maintaining the dissociation. If the near and distance deviations equalize (within 10 PD)
812 or if near exceeds distance, the type of IXT is classified as **pseudo divergence excess**
813 **type**. Otherwise, the type IXT is classified as **true divergence excess type**.

814

815

816 2.4 Historical Information

817 Historical information elicited will include the following: date of birth, gender, race, ethnicity,
 818 prior treatment, and spectacle correction. In addition, investigators will be asked to provide the
 819 reason(s) for performing surgery.

820

821 2.5 Examination Procedures at the Enrollment Visit

822 1. Health-Related Quality of Life Questionnaire: Health-related quality of life (HRQOL) will be
 823 assessed using the Intermittent Exotropia Questionnaire (IXTQ).¹⁵ This questionnaire
 824 consists of 3 components:

- 825 1. Child questionnaire (for children ages 5 years or older) – consists of 12 items which
 826 assess how the child feels about his/her eye condition.
 - 827 ○ The version for children aged 5 to < 8 years has a three-level response scale (not at
 828 all, sometimes, a lot) and is administered by clinical staff either verbally or using a
 829 matching card.
 - 830 ○ The version for children aged 8 years and older has a five-level response scale
 831 (never, almost never, sometimes, often, almost always) and is self-administered.
 832 However, it may be administered verbally by clinical staff if the child cannot read
 833 the questionnaire by him- or herself.

- 834 ○ If possible, children should be positioned such that they are unable to view their
835 parents during testing and parents should be advised not to influence their child's
836 responses.
837 ○ Children 4 years and younger will not complete a child questionnaire.
- 838 2. Parent proxy questionnaire – consists of 12 items which assess how the parent feels the
839 child's eye condition affects the child.
840 ○ The questionnaire has a five-level response scale (never, almost never, sometimes,
841 often, almost always) and is self-administered.
- 842 3. Parental questionnaire – consists of 17 items which assess how the child's eye condition
843 affects the parent.
844 ○ The questionnaire has a five-level response scale (never, almost never, sometimes,
845 often, almost always) and is self-administered.
- 846 2. Stereoacuity Testing: stereoacuity will be assessed in current refractive correction using the
847 following:

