Although complete or near-complete resolution was specified post hoc, a three-level failure/indeterminate/success outcome was prespecified in the protocol; the only difference between the “success” level and “complete or near-complete resolution” is that patients who met suboptimal outcome criteria at a previous visit but not at the 3-year visits were considered failures in the pre-specified outcome but could potentially be considered complete or near-complete resolutions if all other criteria were met.

127 The treatment group difference in the proportion of participants with complete or near complete resolution
128 at 3 years was compared using Barnard’s exact test and calculating a 95% CI using Farrington-Manning
129 scores. Originally the Fisher’s exact test was used, but the corresponding exact CI is calculated in a way
130 in SAS that would permit potential disagreements on statistical significance between p values of <0.05
131 and the 95% CI, whereas Barnard’s test and Farrington-Manning scores for the 95% CIs will agree on
132 statistical significance.

133
134 Note that complete or near-complete resolution *without meeting suboptimal surgical outcome at any time*
135 was also reported in the manuscript (consistent with the prespecified “success” criteria in the protocol)
136 and compared between treatment groups using similar methods.

137 138 **1.6 IXT Questionnaire (IXTQ)**

139 For the IXTQ proxy questionnaires and for each of the three parent questionnaire subscales (psychosocial,
140 functional, and surgical), mean Rasch-based QOL scores at 3 years were compared between treatment
141 groups using linear regression models adjusting for the baseline score.

142 For the IXTQ child questionnaire, because some participants were too young for the IXTQ at baseline
143 (those enrolled 3-<5 years of age) and because some children completed the 5 to 7-year old IXTQ version
144 at baseline and the 8 years and older version at 3 years, the two age versions were evaluated separately
145 and mean QOL scores at 3 years were compared between treatment groups using linear regression models
146 that did not adjust for baseline. Because the Rasch scores can be difficult to interpret, the mean of the 0 to
147 100 scores based on the Rasch scores will be cited as the mean in each treatment group.

148
149 The assumptions of ANOVA/ANCOVA will be tested and if violated, a non-parametric test such as
150 Wilcoxon rank sum test will be used.

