*IXT1 IXTQ;
```

552

```
libname IXTQ 'F:\user\PEDIG\Manuscripts-
```

553

```
Presentations\Manuscripts\IXT\IXT2\IXTQ\Manuscript Analysis\Datasets';
```

554

- Contains one record per IXTQ completed at enrollment and 3 years for both IXT1 and IXT2 studies.

555

556

- Take enrollment and 3-year questionnaire scores for IXT1 patients from **IXTQ.IXTQALL_19OCT2017** and add to ROSTER dataset.

557

558

- Scores are also included as follows:

559

- a. For the child IXTQ component, 5 to 7 year version scores are include for children aged 5 to 7 at the time of testing; 8 year and older version scores are include for children aged 8 or older at the time of testing; no child component scores are included for children younger than 5 years at the time of the visit. The variable AGE indicates the child's age at the time of testing.

560

561

562

563

564

- b. For the parent proxy IXTQ component

565

- c. For the parent IXTQ component: each of the three parent IXTQ subscales of psychosocial, function, and surgery.

566

567

- For each IXTQ component or subscale, a Rasch-based score and a 0 to 100 score (based on Rasch score) are included.

568

569

- Note that some participants were too young for the IXTQ at baseline (those enrolled 3-<5 years of age) but completed the 5 to 7 year old IXTQ version at interim visits and at the 3-year visit once the child turned 5 years old. Also note that some children completed the 5 to 7 year old IXTQ version at baseline and the 8 years and older version at 3 years.

570

571

572

573

574

2. Test ANOVA/ANCOVA assumptions for normality, homogeneity of variance, and homogeneity of slopes.

575

576

- Test for normality using Shapiro-Wilkes test

576

```
577 %macro normalitytest (outcome);  
578 %sort (roster, trtgroup);  
579 proc univariate data = roster normal;
```

```

580         var &outcome;
581         by trtgroup;
582     run;
583     %mend;
584

```

```

585     %normalitytest (ParentPsychRaschMean_36);
586     /* Note that all look non-normal(Shapiro-Wilkes test P values all < 0.05 */

```

- Test for homogeneity of variance using Levene's test

```

588     %macro variancetest (outcome);
589     proc glm data = roster;
590         class trtgroup;
591         model &outcome = trtgroup;
592         means trtgroup / hovtest=levене(type=abs) hovtest=bf;
593         title1"ASSESSING ASSUMPTION OF EQUALITY OF VARIANCES FOR '&OUTCOME'";
594     run;
595     quit;
596     %mend;
597

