598     %variancetest (ParentPsychRaschMean_36);
599

```

```

600     /* Note that all look OK except for child younger -- not equal */

```

- Test for homogeneity of regression slopes using regression model with interaction term

```

602     %macro slopetest (outcome, predictor);
603     proc glm data = roster;
604         class trtgroup;
605         model &outcome = trtgroup &predictor trtgroup*&predictor;
606         title1"ASSESSING ASSUMPTION OF EQUALITY OF SLOPES FOR '&OUTCOME' BY INCLUDING
607         INTERACTION TERM IN THE ANCOVA MODEL";
608     run;
609     %mend;
610
611     %slopetest (ParentPsychRaschMean_36, ParentPsychRaschMean_0);
612
613     /* all look OK */
614

```

- 615
3. For each of the two age-specific child IXTQs, the IXTQ proxy questionnaire, and for each of the three parent questionnaire subscales (psychosocial, functional, and surgical), compare distribution of Rasch-based QOL scores at 3 years using Wilcoxon Rank Sum test.

```

616
617
618
619
620     %macro wilcoxon (outcome);
621     proc npariway data = roster plots=none wilcoxon;
622         class trtgroup;
623         var &outcome;
624         title1"NONPARAMETRIC WILCOXON RANK SUM COMPARING '&OUTCOME' BETWEEN TREATMENT
625     GROUPS";
626     run;
627     %mend;
628
629     %wilcoxon (ProxyRaschMean_36);
630

```

- 631 4. Since all analyses have at least one assumption violated, switch to using non-parametric Wilcoxon
632 rank sum test to compare distributions between treatment group, instead of means using ANOVA
633 or ANCOVA.
- 634
- 635 5. Calculate median of median 0 to 100 score at 3 years using proc means.
636

637 **References**

638 ¹Leske DA, Holmes JM, Melia M, on behalf of Pediatric Eye Disease Investigator Group. Evaluation of
639 the Intermittent Exotropia Questionnaire using Rasch analysis. *JAMA Ophthalmol* 2015;133:461-5.

640 ²Leske DA, Hatt SR, Liebermann L, Holmes JM. Evaluation of the Adult Strabismus-20 (AS-20)
641 Questionnaire Using Rasch Analysis. *Invest Ophthalmol Vis Sci* 2012.

642 ³Leske DA, Hatt SR, Liebermann L, Holmes JM. Lookup Tables Versus Stacked Rasch Analysis in
643 Comparing Pre- and Postintervention Adult Strabismus-20 Data. *Transl Vis Sci Technol* 2016;5:11.
644

645 **Datasets used: ROSTER, IXTQALL_19OCT2017**
646

647 **Objective #6: Tabulate non-surgical treatment prescribed for BLR and R/R treatment groups**
648 **separately**

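### IXTQ proxy score and three parent subscales: the rank-test fallback drops a baseline score that was planned for and collected

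*SAP*

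**What the plan says.** SAP of May 30, 2018, section 1.6, compares mean 3-year Rasch scores for the parent proxy form and the psychosocial, functional and surgical parent subscales between "groups using linear regression models adjusting for the baseline score". The two child versions were planned without baseline adjustment, because some children were too young for the form at enrollment and others changed age version by 3 years.

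The fallback rule in the same section reads "The assumptions of ANOVA/ANCOVA will be tested and if violated, a non-parametric test such as" and continues "Wilcoxon rank sum test will be used". Wilcoxon is given as an example. The rule does not say whether the baseline is to be kept.

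The Objective #5 Technical Plan records the results of the checks:

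- Normality, tested on the 3-year score by arm: "Note that all look non-normal(Shapiro-Wilkes test P values all < 0.05".
- Equality of variances: "Note that all look OK except for child younger -- not equal".
- Equality of slopes, tested for parent and proxy scores with calls such as "slopetest (ParentPsychRaschMean_36, ParentPsychRaschMean_0": no problem noted.

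It concludes: "Since all analyses have at least one assumption violated, switch to using non-parametric Wilcoxon". The Wilcoxon macro takes the treatment group and the 3-year score, and nothing else. Only the proxy call is printed, but step 3 applies the test to all six IXTQ comparisons.

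**The concern.** Four of the six IXTQ comparisons were designed to use the pre-randomization score, and as coded they do not. Step 1 of the Technical Plan merges enrollment scores into ROSTER, and the slope check uses one of them. The baseline then drops out without a stated reason.

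For these four scores, non-normality is the only violation recorded. That is a reason to work with ranks, not to discard a covariate whose slopes passed. The check is also on the wrong quantity, since ANCOVA assumes normal residuals rather than normal raw outcomes within arm.

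The other continuous 3-year outcomes keep their baseline: control and PACT in section 1.8 of the March 2017 SAP, stereoacuity in section 1.4 of the May 2018 SAP. Quality of life is a named secondary outcome in protocol section 6.2.4. What is at stake is precision, and adjustment for chance baseline imbalance, on these four scores.

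**Working it through.** **Inputs from the documents.** 101 BLR and 96 R/R patients (May 2018 SAP, section 1.2). The protocol's planning value for loss is 10% (section 6.7). No IXTQ sample size, power, SD, effect, 3-year completion or baseline correlation is stated, so there is no figure of the plan's own to reproduce. The correlation ρ is varied as an assumption.

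**Large-sample size of the effect.** Assume 10% loss: n1 = 101 × 0.9 = 90.9 and n2 = 96 × 0.9 = 86.4. The detectable difference at 80% power, two-sided 5%, without adjustment is (1.96 + 0.84) × √(1/90.9 + 1/86.4) = 0.421 SD. Linear adjustment multiplies this by √(1 − ρ²):

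- ρ = 0.3: 0.402 SD
- ρ = 0.5: 0.365 SD
- ρ = 0.7: 0.301 SD

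The variance ratio, unadjusted to adjusted, is 1/(1 − ρ²): 1.10, 1.33 and 1.96.

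**Rank version.** Rank the 3-year scores and the baseline scores over both arms and centre both. Take b = Σ(rx·ry)/Σ(rx²), form residuals ry − b·rx, and compare them by arm.

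**Simulation.** Assumptions: 80 per arm, lognormal scores (sigma 0.7), a 0.4 SD shift on the underlying normal scale, 5,000 runs per row. The last two columns have 10% of baselines missing at random. Power:

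| ρ | Wilcoxon | Planned ANCOVA | Rank ANCOVA, complete baselines | Rank ANCOVA, complete-case | Rank ANCOVA, mean-rank fill |
|---|---|---|---|---|---|
| 0 | 0.691 | 0.612 | 0.688 | 0.644 | 0.690 |
| 0.2 | 0.693 | 0.617 | 0.702 | 0.656 | 0.700 |
| 0.3 | 0.687 | 0.638 | 0.723 | 0.678 | 0.719 |
| 0.5 | 0.697 | 0.709 | 0.801 | 0.752 | 0.790 |
| 0.6 | 0.693 | 0.764 | 0.856 | 0.812 | 0.842 |

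Mean-rank fill minus Wilcoxon is −0.001, 0.007, 0.032, 0.093 and 0.149. Rejection under the null is 0.046 to 0.053 for all methods. The rank results do not depend on the skew chosen, because ranks are unchanged by a monotone transformation.

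**Sensitivity** (2,500 runs; Wilcoxon / rank ANCOVA with mean-rank fill):

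| Scenario | ρ = 0 | ρ = 0.3 | ρ = 0.5 | ρ = 0.6 |
|---|---|---|---|---|
| 30% of control-arm 3-year scores at the ceiling | 0.650 / 0.648 | 0.646 / 0.666 | 0.636 / 0.732 | 0.644 / 0.779 |
| 0.3 SD shift | 0.446 / 0.442 | 0.436 / 0.462 | 0.437 / 0.533 | 0.464 / 0.604 |
| 90 per arm, 0.4 SD shift | 0.739 / 0.736 | 0.744 / 0.773 | 0.766 / 0.838 | 0.740 / 0.885 |

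The Monte Carlo standard error is at most √(0.25/2500) = 0.010, so the differences at ρ = 0 are noise.

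**Would a residual check have changed the decision?** In the skewed simulations the Shapiro-Wilk test also rejected on the ANCOVA residuals in 100% of runs. Correcting the check may leave the switch to ranks in place, so the main question is which rank test to use.

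**Are baselines available?** Protocol section 2.5 sets an age limit for the child form only: "Children 4 years and younger will not complete a child questionnaire". Proxy and parent baselines are therefore not missing by design on account of age.

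**The case against.** The strongest reply is that the SAP does what it says. Wilcoxon is the only fallback test it names, and it is run after recorded violations. On the skewed scores simulated above it beats the planned ANCOVA at correlations 0 to 0.3 (0.69 against 0.61 to 0.64) and nearly matches it at 0.5. The shortfall therefore exists only against a test the SAP does not name. All of this stands. No departure from the plan, invalidity or loss against ordinary ANCOVA is claimed.

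The gain depends on an unknown correlation between a pre-surgical score and one taken 3 years later. This also stands: at 0 to 0.2 the gain is at most about 1 point. Nor is rank ANCOVA better in every form. Done complete-case with 10% of baselines missing, it loses 4 to 5 points at 0 to 0.2. The advice depends on the mean-rank fill, which shows no loss beyond simulation error at any correlation tried.

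Changing the test now would be a choice made after the data. The SAP's first version took effect on 5/14/18, after the June 2017 closeout database. But the code comments show that Wilcoxon was itself chosen after looking at the 3-year scores. The objection applies to both tests, and reporting both answers it.

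Finally, one test for all six comparisons is simple, and a residual-rank test gives no effect estimate. The coded Wilcoxon gives no adjusted estimate either, and the planned medians can still be reported beside the rank ANCOVA p value.

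**Conclusion.** The concern holds as a point of efficiency. For the proxy score and the three parent subscales, the coded fallback leaves out a baseline that was planned as a covariate and is in the dataset. A rank ANCOVA fits the SAP's open wording. With the mean-rank fill, the gain over Wilcoxon in the main simulation is nil at correlation 0, about 3 points at 0.3, 9 at 0.5 and 15 at 0.6, with type I error near 5%. These figures rest on assumed numbers per arm, shift, missingness and correlation. The sponsor holds the data that would settle the correlation. The change is worth making, but the existing Wilcoxon results remain valid without it.

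**What to change.** In Objective #5, for the proxy score and the three parent subscales:

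1. Name rank ANCOVA as the fallback: regress ranks of the 3-year Rasch score on ranks of the baseline Rasch score and compare the residuals by arm.
2. Give patients without a baseline form the mean baseline rank, so that the analysis set is the same as for Wilcoxon.
3. Run the normality check on the ANCOVA residuals.
4. Report the unadjusted Wilcoxon test beside it as a sensitivity analysis, and state that the choice of fallback was made after 3-year data were available.

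Keep Wilcoxon for the two child versions.

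The cost is a few lines of code on data already in ROSTER, plus one extra result for each of four scores. If the baseline correlation is near zero, the change brings nothing.

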848 • Preschool Randot stereotest at near (performed at 40 cm): If stereoacuity is worse than 40
849 arcsec, it must be retested and the better of the 2 measurements will be used for
850 eligibility.
851 • Distance Randot stereotest (performed at 3 meters)
852 • Titmus Fly & Circles stereotest at near (performed at 40 cm) (note: Animals are not
853 tested)

854 Stereoacuity should be tested before any other clinical testing. If stereoacuity is not tested
855 first, the patient must take a 10 minute break following any dissociative testing (e.g., visual
856 acuity or ocular alignment) prior to testing stereoacuity.

- 857 3. Control of exodeviation: Control of exodeviation will be measured in current refractive
858 correction at distance and near using the Office Control Score.¹⁶
859 • Distance (6 meters) - fixating on an accommodative target such as a video for younger
860 children or reading optotype letters for older children
861 • Near (1/3 meter – fixating on Lang-near viewing stick or similar accommodative target)

862
863 The scale below applies to both distance and near.

864 Intermittent Exotropia Control Scale¹⁶

- 865 5 = Constant Exotropia
866 4 = Exotropia > 50% of the 30-second period before dissociation
867 3 = Exotropia < 50% of the 30-second period before dissociation
868 2 = No exotropia unless dissociated, recovers in > 5 seconds
869 1 = No exotropia unless dissociated, recovers in 1-5 seconds
870 0 = No exotropia unless dissociated, recovers in < 1 second (phoria)

- 871
872 • Levels 5 to 3 are assessed during a 30-second period of observation first at distance
873 fixation and then assessed at near fixation for another 30-second period.
874 • If no exotropia is observed during the 30-second period of observation, levels 2 to 0 are
875 then graded as the worst of three rapidly successive trials:
876 1. An occluder is placed over the right eye for 10 seconds and then removed,
877 measuring the length of time it takes for fusion to become re-established.
878 2. The left eye is then occluded for a 10-second period and the time to re-establish
879 fusion is similarly measured.

- 880 3. A third trial of 10-second occlusion is performed, covering the eye that required the
881 longest time to re-fuse.
- 882 • The worse level of control observed following the three 10-second periods of occlusion
883 should be recorded. If the patient has a micro-esotropia by SPCT but an exodeviation by
884 PACT, the scale applies to the exodeviation.

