1.5 Complete or Near-complete Resolution at 3 Years

Complete or near-complete resolution at 3 years was defined post hoc as meeting all of the following at the 3-year visit:

1. Exodeviation <10 PD (tropia, phoria, or no deviation) by both SPCT and PACT at distance and near and ≥ 10 PD reduction in PACT magnitude from distance and near angles at enrollment provided the corresponding angle was at ≥ 10 PD at baseline.
 - This criterion was originally written as ≥ 10 PD reduction in PACT magnitude from *largest of* distance and near angles at enrollment. After asking the protocol chairs to clarify which angle needed to be reduced by ≥ 10 PD at 3 years in cases where the distance and near angles at enrollment are the same magnitude (i.e. neither is the ‘largest’), it was decided that both angles should be reduced by ≥ 10 PD in order to meet the criterion, if the angle was at ≥ 10 PD at baseline, OR should be reduced to orthodeviation (0 PD) if the angle was at <10 PD at baseline. *Note that because all patients in the basic primary cohort have distance and near PACT ≥ 10 PD, this caveat is not cited in the manuscript as being part of the criteria. Only one patient in one of the secondary cohorts was <10 PD at baseline—a 3 PD near angle which was ortho at 3 years.* The revised criterion was extended to all patients, not only those whose enrollment PACT was the same magnitude at distance and near, for consistency. For example, if a patient with 20 PD at distance and near at baseline is required to have a reduction ≥ 10 PD at both distance and near at 3 years in order to be eligible to meet complete or near-complete resolution, then a patient with 25 PD at distance and 15 PD at near should also be required to have both reduced by ≥ 10 PD at 3 years, otherwise the first patient is being penalized simply for having the same measurement at both distances.
2. Esotropia <6 PD (tropia or no tropia, *note that phoria does not apply to SPCT*) at distance and near by SPCT
3. No decrease in Preschool Randot stereoacuity of ≥ 2 octaves from the enrollment stereoacuity or to nil
4. No reoperation or treatment with botulinum toxin
5. No non-surgical treatment for a recurrent or residual exodeviation

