151 152 153 **1.8 Nonsurgical Treatment**

154 Postoperative nonsurgical treatment for XT, ET, and/or diplopia was tabulated for each treatment group.
155 Because the reason for this nonsurgical treatment was not specified other than being prescribed for IXT,
156 ET, or diplopia, the type of deviation that was present when the nonsurgical treatment was prescribed was
157 reported. This data was used to report the proportions of participants with non-surgical treatment
158 prescribed when exodeviation was present, when esodeviation was present and when exodeviation and
159 esodeviations were present at different times during the study. Among participants who met the constant
160 esotropia suboptimal surgical outcome during the study, the proportion who had nonsurgical treatment
161 prescribed was reported.

162 163 **1.7 Additional Tabulations and Analyses**

164 The following will be tabulated for each treatment group:

- 165 • Baseline demographic and clinical characteristics
- 166 • Baseline demographic and clinical characteristics for study completers vs. not
 - 167 ○ Study completion refers to patients who completed the 3-year visit or were withdrawn
 - 168 from the study after they met the primary outcome of suboptimal surgical outcome (for
 - 169 meeting objective criteria or for reoperation). It does not include patients who were
 - 170 withdrawn from the study without ever having met primary outcome of suboptimal
 - 171 surgical outcome.
- 172 • Percentage with completion of each follow up visit

173
174
175
176
177
178
179
180
181
182
183
184
185
186
187

- Listing of each complications that occurred either during surgery, or were reported at the 1-week or the 8-week postoperative visits
- Outcomes for participants meeting exotropia or esotropia suboptimal outcome criteria
 - Separately for participants who met the exotropia and esotropia components of suboptimal outcome criteria, the proportion out of those meeting the criterion who received nonsurgical treatment, and the proportion of non-reoperated cases in which the criterion of interest was not present at 3 years was reported.
- In subjects who completed the 3-year visit, 3-year status was evaluated according to whether suboptimal surgical outcome had occurred before 3 years

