649 **1. Define nonsurgical treatment of interest as that which was prescribed for XT, ET, or**
650 **diplopia.**

651 Because the reason for this nonsurgical treatment was not specified other than being prescribed for
652 XT, ET, or diplopia, the type of deviation that was present when the nonsurgical treatment was
653 prescribed was reported. This data was used to report the proportions of participants with non-
654 surgical treatment prescribed when exodeviation was present, when esodeviation was present, and
655 when exodeviation and esodeviations were present at different times during the study. Among
656 participants who met the constant esotropia suboptimal surgical outcome during the study, the
657 proportion who had nonsurgical treatment prescribed was reported.

658
659 Do not include nonsurgical treatment prescribed for amblyopia, which was recorded in a different
660 section of the data form.

661
662 **2. Obtain alignment data**

663
664 **3. Create patient level flag variables for the following:**

- 665 • Nonsurgical treatment when XT is present anytime during study
- 666 • Nonsurgical treatment when ET is present anytime during study
- 667 • Non-surgical treatment when XT and ET are present (different times during study)

668 **Technical Plan**

669 **1. Get treatment prescribed records from the SQL data table TBLIXT1TREATRX. Obtain**
670 **visit date from the login table.**

671 Use: NonSurgTmtRxNone, NonSurgTmtRxPrism, NonSurgTmtRxPatch,
672 NonSurgTmtRxOverMinus, NonSurgTmtRxVT, NonSurgTmtRxOther, NonSurgTmtRxOtherDs

673
674 Do not use: AmbTrtRxNone, AmbTrtRxPatch, AmbTrtRxAtrp, AmbTrtRxVT,
675 AmbTrtRxOverPlus, AmbTrtRxBang, AmbTrtRxOther, AmbTrtRxOtherDs

676
677 **2. Obtain SPCT and PACT alignment data for maskedexams from verified dataset**
678 **MASKEDEXAMS. Obtain similar data from the 1 week and 8 week visits from the SQL**
679 **data table TBLIXT1OCUALIGN.**

680
681 Consider XT present if exotropia is present by SPCT or exodeviation is present by PACT
682 Consider ET present if esotropia is present by SPCT or esodeviation is present by PACT

683
684 Merge alignment data into treatment prescribed records.

685
686 **3. Create patient level flag variables for the following:**

687

- Nonsurgical treatment when XT is present anytime during study

688

- Nonsurgical treatment when ET is present anytime during study

689

- Non-surgical treatment when XT and ET are present (different times during study)

690

691

692

693

694

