695

1. Loop through the treatment prescribed records, retaining flags for non-surgical treatment when XT is present and for non-surgical treatment when ET is present.
2. Take last record for each patient.
3. Add flags to roster dataset.
4. Create flag for non-surgical treatment when XT and ET using XT and ET treatment flags .

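### The May 2018 SAP counts exotropia and esotropia treatment at a single visit as treatment at different times, and does not say which variable decides criterion 5 of complete or near-complete resolution

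*SAP*

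**What the plan says.** Objective #6 of the May 2018 SAP tabulates non-surgical treatment by arm. The indication is unknown: "Because the reason for this nonsurgical treatment was not specified other than being prescribed for" exotropia, esotropia or diplopia. Section 1.8 and Objective #6 therefore report the deviation found when treatment was prescribed.

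Technical Plan step 2 defines the two states: "Consider XT present if exotropia is present by SPCT or exodeviation is present by PACT" and "Consider ET present if esotropia is present by SPCT or esodeviation is present by PACT". Alignment is taken from the masked exams and from the 1-week and 8-week visits.

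Step 3 carries one XT flag and one ET flag per child across all treatment records and adds them to ROSTER. A third variable is described as "Non-surgical treatment when XT and ET are present (different times during study" and is derived by this instruction: "Create flag for non-surgical treatment when XT and ET using XT and ET treatment flags".

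Separately, criterion 5 of complete or near-complete resolution (section 1.5) reads "No non-surgical treatment for a recurrent or residual exodeviation". Objective #4 adds that treatment for esodeviation does not disqualify a child. It names its input as non-surgical treatment for IXT and lists ROSTER as its dataset.

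**The concern.** The two states are not mutually exclusive. A child can have esotropia at one distance and exodeviation at the other, or esotropia by SPCT with exodeviation by PACT. Protocol section 2.5, item 3, anticipates the second pattern: "If the patient has a micro-esotropia by SPCT but an exodeviation by" PACT. One treatment record in such a child sets both flags.

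Two things follow. First, the reported count of children treated with exo- and esodeviation at different times will include some who had both at one visit. Second, criterion 5 needs treatment for exodeviation to be separated from treatment for esodeviation, and the SAP does not say how that is done. If the XT flag does the work, prism given for an esotropia could cost a child resolution status that criterion 5 means to preserve.

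**Working it through.** The plan gives no figure on this point to reproduce. The check applies the written rules and sets the relevant sections side by side.

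**1. How easily one visit sets both flags.** Assumptions: a deviation is present if found at distance or near; exotropia by SPCT implies exodeviation by PACT; esotropia by SPCT may go with esodeviation or exodeviation by PACT (Protocol 2.5, item 3).

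- Possible SPCT/PACT pairs at one distance: exo/exo, none/exo, none/zero, none/eso, eso/eso, eso/exo. That is 6, so 6 × 6 = 36 patterns over distance and near.
- Three pairs contain no exo sign, so 3 × 3 = 9 patterns leave XT unset. Likewise 9 leave ET unset, and 1 leaves both unset.
- Patterns setting both flags: 36 − 9 − 9 + 1 = 19.
- Patterns with esotropia by SPCT at either distance: 36 − 4 × 4 = 20. Of these, 9 − 2 × 2 = 5 leave XT unset, so 15 of 20 also set XT.

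These are counts of sign patterns. They are not frequencies of children.

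**2. The combined flag.** Child A has one treatment record, at a visit with both deviations: XT = 1, ET = 1. Child B has two records on different dates, one with exodeviation only and one with esodeviation only: XT = 1, ET = 1. The combined flag sees only those two values and is the same for both children. Its description fits B alone.

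**3. Criterion 5.** Objective #4 calls for non-surgical treatment for IXT. Section 1.8 and Objective #6 say the reason was not recorded at that level, so no recorded variable supplies this input directly. The Objective #6 flags are the only deviation-specific treatment variables that the SAP defines, and they are stored in the dataset that Objective #4 uses. Objective #4 does not cite them.

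**4. Records without alignment.** Protocol 4.1 allows non-surgical treatment at any time, and 4.6 allows extra visits. The March 2017 SAP (Objective #2, step 2) excludes masked-exam records for unspecified visits where the exam was not required or not done. A treatment prescribed at such a visit has no alignment to merge and, as written, sets neither flag. No rule covers it.

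**5. Size per child.** The arms are 96 (R/R) and 101 (BLR). One misclassified child who otherwise qualifies moves R/R by 1/96 = 1.04 points or BLR by 1/101 = 0.99 points. The resolution analysis is limited to children who completed the 3-year visit. With the protocol's 10% planning allowance for loss (section 6.7), taken here as an assumption about non-completion, the denominators are about 86 and 91. The shifts are then 1/86 = 1.16 and 1/91 = 1.10 points.

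**The case against.** The strongest reply is that Objective #6 assigns no indication. It says openly that the reason was not recorded and words its flags as treatment when a deviation is present. Read that way, two overlapping flags are an accurate description. This stands for the two single flags. It does not rescue the combined flag, whose description its construction does not deliver.

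A second reply is that Objective #4 never cites these flags and expressly permits treatment for esodeviation. It could have required XT without ET, or used case review. This also stands. A reader might infer that the SAP does remove such children from resolution. The documents show only that the derivation is unstated and that the XT flag is the obvious candidate.

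The exposed group is also narrower than the pattern counts suggest. Protocol 4.4.1 mandates prism at 8 weeks for constant esotropia at both distances; with esodeviation by PACT at both, XT is not set at that visit. A child with constant esotropia of at least 6 PD, confirmed at a masked exam from 6 months on, is already a surgical failure and so is outside the no-previous-failure version whatever criterion 5 says. The alignment gap is limited to visits without a masked exam, and nothing shows how many prescriptions fall there.

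A reader might also infer bias against R&R, because Protocol 6.6 expects overcorrection there. That section concerns surgical failure, from esotropia that prism cannot manage. It gives no expected prism use by arm and supports no direction of bias.

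**Conclusion.** The combined flag is wrong as specified: a single visit with both deviations satisfies a category described as different times. That conclusion needs no assumption beyond the possibility of both deviations at one visit, which the protocol recognises.

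For complete or near-complete resolution, the finding is an unspecified derivation. Harm depends on the XT flag being used for criterion 5 without a rule for overlap. In that case both versions of the outcome are exposed, the post hoc one and the one presented as consistent with the protocol's success criteria. Each affected child who otherwise qualifies moves an arm by about 1 percentage point, from 0.99 to 1.16 on the denominators above. The documents do not give the number of such children, so neither a total nor a direction can be stated. The primary outcome does not use non-surgical treatment and is unaffected.

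**What to change.** 1. Set the combined flag only when the XT and ET treatment records have different visit dates. Report same-visit overlap as its own category.
2. Name the variable used for criterion 5. Where ET was also present at the visit, the XT flag alone should not disqualify a child without a stated rule.
3. Report treatment records with no alignment data as unclassified.
4. Add sensitivity analyses of both resolution outcomes: one in which any non-surgical treatment for exotropia, esotropia or diplopia counts as not resolved, and a pair in which same-visit overlaps count first as exodeviation treatment and then as esodeviation treatment.

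Letting the SPCT tropia always decide is a tempting shortcut but not a safe one. It would code a micro-esotropia with a large exodeviation by PACT as esotropia treatment, although Protocol 2.5 applies the control scale to the exodeviation in that pattern.

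The cost is SAP wording and re-derivation of a few variables. Objective #6, step 1, already retrieves the visit date, and no new data are needed. The small downside is that the indication remains inferred; the sensitivity analyses show how much depends on that.
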